3.3 Eligibility Criteria

Patients must have baseline conditions reviewed prior to enrolling and must meet all inclusion and exclusion criteria. In addition, the patient must be thoroughly informed about all aspects of the study, including the required post-operative follow up. Written informed consent must be obtained from the patient prior to enrollment. Per standard of care, patients will not receive chemotherapy or radiation treatment within 4 weeks of the operation. The following criteria apply to all patients enrolled into the study unless otherwise specified.

3.3.1 Inclusion Criteria

In order to be eligible to participate in this study, an individual must meet all of the following criteria:

1. Histologically confirmed breast malignancy OR increased risk for breast cancer

2. Age \geq 18 years
3. Scheduled to undergo bilateral mastectomy with plastic surgery closure or reconstruction
4. Ability to understand a written informed consent document, and the willingness to sign it
5. At least 4 weeks post-completion of chemotherapy or radiation therapy

3.3.2 Exclusion Criteria

An individual who meets any of the following criteria will be excluded from participation in this study:

1. Any significant medical condition or laboratory abnormalities, which places the subject at unacceptable risk if she were to participate in the study
2. Any history of thromboembolic disease
3. Current anticoagulant use
4. Current use of chlorpromazine due to label contraindication
5. Current use of any prothrombotic medical products due to label contraindication
6. Documented or reported allergic reaction to tranexamic acid
7. Male patients

3.4 Inclusion of Women and Minorities

3.4.1 Eligibility of Women and Minorities

Women of any race, or ethnicity are eligible for this study

3.4.2 Recruitment of Minority Groups

The study recruitment strategy aims to achieve representation of minority groups that reflects the demographics of the affected population in the catchment area at UCSF.

3.5 Inclusion Across the Lifespan

3.5.1 Age Range of Participants

Individuals ages 18 and over are eligible for this study. Children are excluded from the study because insufficient data on prospective benefits and/or adverse events for a treatment and the disease/condition is extremely rare in children

3.5.2 Study Design/Recruitment Considerations Related to Age Groups

The study design and recruitment strategy aim to achieve representation of age groups that reflect the demographics of the affected population

3.6 Duration of Treatment

All patients in this study will receive topical TXA applied to one breast intraoperatively during the study. They will only have the one exposure to the treatment at the time of surgery.

Bilateral Mastectomy Patients

During surgery, after removal of breast  **tissue and prior to closure**

One side Breast Skin Flap: soaked with 20ml of 25mg/ml TXA solution
One side Breast Skin Flap; soaked with 20ml of 0.9% normal saline (control)

3.7 Duration of Follow Up

Patients are routinely followed for at least one year after undergoing post-mastectomy breast reconstruction and monitored for the development of any of the outcomes of interest and assessed for drain removal. Patients in this trial will be seen per our standard follow-up care, which typically involves a post-operative visit in the 1-4 week period, in the 5-11 week period, and some time in the 12 week to 1 year period. The exact number and schedule of visits vary by patient and their needs. Our study-specific assessment and procedures will occur at each of these regularly scheduled visits up to one year after surgery. Regarding AEs, Given the mechanism of action of TXA, there is the theoretical complication of perpetuating thrombotic events due to inhibition of clot breakdown[16]. There have been no documented events of venous thromboembolism in relation to topical administration of TXA in plastic surgery procedures, which are the most relevant to our proposed study[6, 8, 14, 15, 18]. Other side effects associated with intravenous tranexamic acid include hypersensitivity reactions, seizures, visual disturbances, and dizziness[16]. The latter three would likely not apply to our study given that with topical tranexamic acid, the drug will not cross the blood brain barrier and thus would not elicit neurologic adverse effects.

However if any patient develops these signs of symptoms, the TXA will immediately be removed from their system via washout in the operating room. If they later develop signs or symptoms of post-operative bleeding, hematoma, or seroma to their breast, they will be cared for per the standard of care which may involve aspiration, drain placement, or return to the operating room. They will not be removed from the study as these AEs are not unacceptable.

Subjects may withdraw consent at any time for any reason. A subject may be withdrawn by the investigator if enrollment into the study is determined inappropriate, the study plan is violated, or for administrative and/or other safety reasons.

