3.1 Characteristics

We propose a prospective, placebo-control trial looking at the effect of topical tranexamic acid on post-operative bleeding, hematoma, seroma, drain output, and bruising in post-mastectomy breast reconstruction. We will recruit patients undergoing bilateral mastectomy at our institution. Patients will be excluded if they have previous history of bleeding or coagulation disorders. Each patient will serve as their own internal control, with one side receiving saline and the other TXA. During surgery and prior to wound closure, we will moisten the wound surface of one side with 20 cc of dilute TXA 25mg/ml solution, and the contralateral with 20cc of saline. Demographics, cancer details, and surgical characteristics will be collected. Outcomes will we assess include hematoma, seroma, reoperation, drain duration, and degree of ecchymosis will be recorded post-operatively for analysis over a 3-month period. The primary outcome will

be presence of hematoma. Secondary outcomes will include seroma, drain output and duration, ecchymosis, and return to operating room.

The surgeon will mix the TXA solution and pass onto the surgical field (detailed in a later section). After completion of the bilateral mastectomy, the plastic surgeon will perform their portion of the procedure. Immediately prior to final closure, 20ml of 25mg/ml TXA solution will be infiltrated into one breast pocket. 20ml of 0.9% normal saline will be infiltrated into the other breast pocket. No other hemostatic agents will be used. The sidedness of the TXA administration will be documented by the surgery team in our record but kept confidential from the surgery clinic staff to prevent bias at post-operative assessments. The solutions will be allowed to dwell while performing incisional closure, and the solutions will be evacuated by the Jackson-Pratt drain when placed to bulb suction at the end of the case. Post-procedure, each patient will be provided with standard post-operative instructions. They will be followed post-operatively for up to 1 year.

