7.2 Safety Analysis

Safety will be assessed by clinically assessing for signs of intolerance or irritation after administration of the TXA. If there are any immediate adverse effects noted related to sensitivity reactions, the JP drain will be placed to suction and the TXA solution removed and washed out via infiltration of plain saline to the breast pocket. We will assess patients at each post-operative visit with condition-specific physical exam and history to make sure there are no other adverse effects noted. If any thrombotic complications are found with no other explanation, we will deem the study unsafe and stop the study.

8 Study Management

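### Sections 3.7, 7.2 and 3.1 do not agree on which reactions trigger removal of TXA, until when, and by what procedure

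*Combined protocol and SAP*

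**What the plan says.** Section 3.7 (Duration of Follow Up) first notes that "there is the theoretical complication of perpetuating thrombotic events due to inhibition of clot breakdown". It then states: "Other side effects associated with intravenous tranexamic acid include hypersensitivity reactions, seizures, visual disturbances, and dizziness". It adds that the last three of these four are unlikely to apply to topical use. The next sentence opens "However if any patient develops these signs of symptoms" and gives the action: "the TXA will immediately be removed from their system via washout in the operating room". Later bleeding, hematoma or seroma is handled separately, by standard care "which may involve aspiration, drain placement, or return to the operating room".

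Section 7.2 (Safety Analysis) gives a narrower trigger: immediate adverse effects related to sensitivity reactions. Its action is that "the JP drain will be placed to suction and the TXA solution removed and washed out via infiltration of plain saline" into the breast pocket. No location is named. For thrombotic complications without another explanation, it says that the study will be stopped and does not mention removal of the drug.

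Section 3.1 (Characteristics) says that "the solutions will be evacuated by the Jackson-Pratt drain when placed to bulb suction at the end of the case". Section 6.3 agrees: drains stay off suction until the end of the case.

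On outcomes, Section 3.1 states: "Secondary outcomes will include seroma, drain output and duration, ecchymosis, and return to operating room". Section 2.2 names reoperation among the outcome measures, and Section 7.1 collects return to the operating room. None of the three says which causes count. The secondary endpoint table in Section 2.3 does not list the outcome.

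**The concern.** Staff facing a possible reaction have two instructions that do not match. A patient with dizziness, a visual disturbance or a seizure meets the trigger in Section 3.7 but not, as worded, the one in Section 7.2. If the sign appears after the operation, Section 3.7 followed literally takes the patient to the operating room to remove a solution that Section 3.1 says the drain has already evacuated. That is a rule with a safety consequence, not just a missing detail.

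There is a smaller consequence for the analysis. TXA goes into one pocket only, so a washout to remove it can occur only on that side. If it happens after the patient has left the operating room, nothing in Sections 2.2, 3.1 or 7.1 says whether it counts as a return to the operating room. Two data abstractors could classify the same event differently.

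**Working it through.** The documents give no figure on this point (no reaction rate and no washout rate), so the check is a comparison of the sections.

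| | Section 3.7 | Section 7.2 | Section 3.1 |
|---|---|---|---|
| Trigger | The signs just described, in any patient | Effects related to sensitivity reactions | Not addressed |
| Onset | No limit; the section covers follow-up to one year | Immediate | Not addressed |
| Action | Washout in the operating room | Drain to suction, then saline infiltration; no location | Routine evacuation by the drain at the end of the case |
| Thrombosis | Included on one reading | Study stops if unexplained; no washout mentioned | Not addressed |

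**Step 1: trigger.** It is unclear which signs Section 3.7 refers back to, so each reading was tested.
- Narrow: only the effects in the sentence immediately before, namely seizures, visual disturbances and dizziness. On its wording, Section 7.2 covers none of these, and the hypersensitivity that it does cover falls outside Section 3.7.
- Middle: those three plus hypersensitivity. The sections overlap on hypersensitivity only.
- Broad: those four plus thrombotic events. The overlap is the same, and Section 7.2 gives thrombosis a different consequence.

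The triggers differ on all three readings.

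**Step 2: timing.** In Section 3.7 the word for immediacy qualifies the removal, not the onset of signs. In Section 7.2 it qualifies the adverse effects. Only Section 7.2 therefore limits onset. Dizziness and visual disturbance are symptoms that a patient reports. Assuming general anaesthesia, they can hardly be noticed before the case ends, so Section 3.7 is naturally read as reaching beyond it.

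**Step 3: action.** While the patient is still on the table, drain suction followed by saline may be exactly the washout that Section 3.7 has in mind, and no conflict need arise. Once the drain has been put to suction and the patient has left, a washout in the operating room is a different act, and by Section 3.1 the solution is no longer there.

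**Step 4: outcome count.** A washout during the index operation is not a return and adds nothing. A washout after the patient has left could add one event on the TXA side and none on the saline side. With the planned 150 breasts per side, one such event moves the TXA-side proportion by at most 1/150 = 0.0067, or 0.7 percentage points. It is at most that because the same breast might have returned for another reason. With no late washouts the effect is zero. Without a documented rate, going on to power or a p-value would only reflect invented inputs.

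**The case against.** The strongest reply is that Sections 3.7 and 7.2 describe a single intraoperative step. Section 3.7 says that the drug is removed at once and then contrasts what happens if bleeding, hematoma or seroma develops later. Section 7.2 speaks of immediate effects and names no location, so it does not contradict the operating room. The solution dwells in the pocket only until the end of the case. This stands for reactions during the index operation. It does not explain why Section 3.7 extends to signs that Section 7.2 omits, or why it sets no onset limit. If early use only was intended, the protocol does not say so.

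A second reply is that stopping the study for thrombosis is a trial-level action, compatible with a separate action for the individual patient. That is fair: Section 7.2 is silent on the patient-level step rather than opposed to it, and whether Section 3.7 includes thrombosis at all is ambiguous.

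On outcomes, a reader might infer that the Section 3.7 washout is itself a return to the operating room and so would be counted against TXA. The documents do not support that. Section 3.7 uses the language of return only for later bleeding, hematoma or seroma. Nor would counting a late washout be an error: a reoperation caused by the study drug belongs in an all-cause comparison. What remains is that the count has no stated rule.

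Adverse event recording already covers part of this. Section 6.1 schedules adverse event assessment during surgery and in every follow-up window, and Appendix 1 enters Grade 3-5 events with attribution. That would probably capture a serious reaction. It does not record why a patient returned to the operating room, and a lower-grade sign that led to a washout might not be entered.

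**Conclusion.** The inconsistency is real and should be corrected. The triggers in Sections 3.7 and 7.2 differ on every reading tested, only Section 7.2 limits onset, and a washout for later signs cannot be squared with the end-of-case evacuation in Section 3.1. For a reaction during the index operation, the difference in action may be one of wording only. This review takes no position on which clinical rule is right.

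The effect on the return-to-operating-room outcome is secondary and conditional. It needs a washout after the patient has left the operating room, and the documents give no frequency for that. The effect is zero if none occurs and at most 0.7 percentage points on the TXA side per event at 150 breasts per side. The documents do not support a claim that the outcome would be biased, or that a significance result would change.

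**What to change.** 1. Reconcile Sections 3.7, 7.2 and 3.1 into one statement, placed once and cross-referenced elsewhere. It should say which events trigger removal of the study solution (including whether thrombotic and neurologic signs are among them), up to what time, and by what procedure. The investigators should set the clinical content.
2. In Section 7.1, keep the all-cause comparison of return to the operating room and add a recording rule. For example: *Each return to the operating room will be recorded with its side, date and main reason (hematoma, seroma, infection or wound problem, removal of study solution for a suspected reaction, other). Removal of study solution for a suspected reaction, whether during or after the index operation, will be recorded as an adverse event and reported separately by count. A removal during the index operation is not a return.*
3. If return to the operating room remains a secondary outcome, add it to the table in Section 2.3 with the same definition.

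The cost is one reconciled paragraph, one reason code on the reoperation form and one table row. Under Section 8.4 the change is an amendment needing committee and IRB approval. Sample size and planned tests are unchanged.

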3.8 Primary Completion

The expected primary completion date is 2 years after the study opens to accrual, as we expect that given the volume of bilateral mastectomies performed at our institution per week, we should be able to reach at least 150 participants in 2 years.

3.9 Study Completion

The expected study completion date is 2 years after the study opens to accrual.

4 Investigational Product- TXA

Tranexamic Acid is an antifibrinolytic that is FDA approved for use in patients with hemophilia for short-term use (two to eight days) to reduce or prevent hemorrhage and reduce the need for replacement therapy during and following tooth extraction [16]. However, it has been used off-label with great efficacy at preventing bleeding and bruising in many other surgical fields both intravenously and topically. This study proposes the topical use of dilute TXA solution.

4.1 Description, Supply and Storage of Investigational Products

4.1.1 Tranexamic Acid

The information in the following section was obtained from the Cyklokapron (Tranexamic Acid) drug label from the FDA [16]

Mechanism of Action

Tranexamic acid is a synthetic lysine amino acid derivative, which diminishes the dissolution of hemostatic fibrin by plasmin. In the presence of tranexamic acid, the lysine receptor binding sites of plasmin for fibrin are occupied, preventing binding to fibrin monomers, thus preserving and stabilizing fibrin's matrix structure.

The antifibrinolytic effects of tranexamic acid are mediated by reversible interactions at multiple binding sites within plasminogen. Native human plasminogen contains 4 to 5 lysine binding sites with low affinity for tranexamic acid ($K_d = 750 \mu\text{mol/l}$) and 1 with high affinity ($K_d = 1.1 \mu\text{mol/L}$). The high affinity lysine site of plasminogen is involved in its binding to fibrin. Saturation of the high affinity binding site with tranexamic acid displaces plasminogen from the surface of fibrin. Although plasmin may be formed by conformational changes in plasminogen, binding to and dissolution of the fibrin matrix is inhibited.

Metabolism

Distribution

The initial volume of distribution is about 9 to 12 liters. The plasma protein binding of tranexamic acid is about 3% at therapeutic plasma levels and seems to be fully accounted for by its binding to plasminogen. Tranexamic acid does not bind to serum albumin.

Elimination

After an intravenous dose of 1 g, the plasma concentration time curve shows a triexponential decay with a half-life of about 2 hours for the terminal elimination phase.

Excretion

Urinary excretion is the main route of elimination via glomerular filtration. Overall renal clearance is equal to overall plasma clearance (110 to 116 mL/min) and more than 95% of the dose is excreted in the urine as the unchanged drug. Excretion of tranexamic acid is about 90% at 24 hours after intravenous administration of 10 mg/kg body weight.

Contraindications

- In patients with subarachnoid hemorrhage, due to risk of cerebral edema and cerebral infarction
- In patients with active intravascular clotting
- In patients with severe hypersensitivity reactions to tranexamic acid or any of the ingredients (4).

Formulation, Appearance, Packaging, and Labeling

Tranexamic Acid is available as a single-dose 1g vial that needs to be reconstituted in 1ml of saline, to thus be 1000mg/ml. This 1g vial is readily available in the anesthesia cart in the operating room. This can then be added to 40cc saline to dilute it to 25mg/ml TXA solution. 20cc of this can then be infiltrated into the breast pocket, for a maximum exposure of 500mg of TXA to any one side

Availability

Tranexamic Acid is readily available at UCSF and stocked in most anesthesia carts in the operating room for perioperative administration in other surgical specialties.

Side Effects

The following side effects apply to intravenous systemic dosage of TXA, and may not necessarily apply to topical application.

- Thromboembolic Risk
- Seizures
- Hypersensitivity Reactions
- Visual Disturbances
- Dizziness

5 Treatment Plan

5.1 Dosage and Administration

Treatment will be administered in the operating room at the time of surgery. 20ml of 25mg/ml solution of TXA will be infiltrated into one of the breast pockets and allowed to dwell in the pocket prior to closure. The other side will receive 20ml of plain 0.9% Saline. This will be the only administration of TXA for the duration of the study.

5.2 Participant Registration

A written, signed, informed consent form (ICF) and a Health Insurance Portability and Accountability Act (HIPAA) authorization must be obtained before any study-specific assessments are initiated. A copy of the signed ICF will be given to the subject and a copy will be filed in the medical record. The original will be kept on file with the study records.

All participants consented to the study will be registered in OnCore®, the UCSF Helen Diller Family Comprehensive Cancer Center Clinical Trial Management System (CTMS). The system is password protected and meets HIPAA requirements.

6 Study Procedures and Schedule of Events

6.1 Study Calendar

The study-specific procedures and assessments are detailed in this section and outlined in the Study Calendar –

Period/Procedure	Screening Period		During Surgery	Assessment Period ³		
	Pre-operative period	Day of Surgery		1-4 weeks	5-11 weeks	12 weeks – 1 year
Study Day/Visit Day						
Informed consent¹	X					
Baseline conditions	X					
TXA Exposure						
Right Breast						
Left Breast			X			
Clinical procedures						
Physical exam		X	X	X	X	X
Vital signs		X	X	X	X	X
Medical history		X				
AE assessment			X	X	X	X
Outcomes assessment²				X	X	X

¹ Informed consent can occur prior to screening window

² Outcomes from clinical exam including hematoma, seroma, infection

³ Patients are scheduled for regular clinic visits up to one year after surgery. Study-specific assessments and procedures will occur at these regularly scheduled visits. The exact timing of these visits varies by patient. If patients have multiple visits scheduled within these assessment windows, study-specific assessments and procedures may be performed at multiple visits on an optional basis

6.2 Participant Registration

A written, signed, informed consent form (ICF) and a Health Insurance Portability and Accountability Act (HIPAA) authorization must be obtained before any study-specific assessments are initiated. A copy of the signed ICF will be given to the subject and a copy will be filed in the medical record. The original will be kept on file with the study records.

All participants consented to the study will be registered in OnCore®, the UCSF Helen Diller Family Comprehensive Cancer Center Clinical Trial Management System (CTMS). The system is password protected and meets HIPAA requirements.

